### 5.9.2 Storage

Ground whole grain flaxseed will be stored by the Investigational Drug Service (IDS) at the University of Pennsylvania in a cool dry place per product instructions protected from direct light.

### 5.9.3 Dispensing of Study Drug

All FS will be dispensed in subject-specific packages in sufficient quantities to allow for the ingestion during the study treatment period. No extra FS will be provided. The subject will be provided with a one week supply of individually packaged FS with clear instructions given at the start of the treatment period to consume. Subjects will be given logs to track FS consumption. The Investigational Drug Service (IDS) at the University of Pennsylvania will dispense flaxseed to research staff that will provide it to the study participants.

### 5.9.4 Return or Destruction of Study Drug

At the completion of the study, there will be a final reconciliation of study materials shipped, consumed, and remaining. This reconciliation will be logged on the reconciliation form, signed and dated. Any discrepancies noted will be investigated, resolved, and documented prior to return or destruction of unused study materials. Materials destroyed on site will be documented in the study files.

## 6 Study Procedures

See Table 1 (Study Flow Chart).

### 6.1 Visit 1: Pre-irradiation (Week -1)

At Visit 1 (Pre-irradiation), subjects will receive information regarding the study and informed consent will be obtained. A baseline CTCAE toxicity evaluation will be performed. Flaxseed and FS log will be distributed to subjects. Subjects will be asked to start daily FS ingestion. A blood sample and urine sample will be obtained for baseline urinary isoprostanes (a marker of oxidative stress) and plasma lignan levels (flaxseed metabolites). The blood sample obtained will be up to 15mL in volume. A buccal swab will also be obtained.

*Please note that radiation is not an experimental question.*

Standard pre-irradiation procedures will be performed as follows:

The radiation dose will be prescribed at mid-separation on the central ray for two equally weighted beams. For all other beam arrangements, the dose will be prescribed at the center of the target area or at the intersection of central rays of the beams.

Simulation for all fields is required. CT-based treatment planning is required for all subjects and will be used to define the target volume. The gross tumor volume (GTV) will consist of all known sites of disease including the primary tumor and all pathologically enlarged ( $\geq 1$  cm in short axis) or FDG-PET positive lymph nodes. Discontinuous volumes are allowed. Elective nodal irradiation is not allowed and therefore the GTV will be equal to the clinical target volume (CTV) for this study. The planning target volume (PTV) will be constructed from the GTV by an automatic margining tool supervised and edited by the treating radiation oncologist. The

CONFIDENTIAL

This material is the property of the University of Pennsylvania. Do not disclose or use except as authorized in writing by the study sponsor.  
Version Date: 07/27/2017

irradiation target volume will be defined by shaped ports with custom-made blocks or multileaf collimation. Portal verification shall be done for all treated fields. Megavoltage equipment is required with minimum peak photon energies of 6 MV. SAD techniques should be used. Each field will be treated every session. Interruptions in therapy should be discussed with the principal investigator but will be instituted at the discretion of the attending radiation oncologist.

Dose calculation should be performed using inhomogeneity corrections to account for differences in tissue density across the thorax. The total dose to gross disease will be **60-70 Gy**. The prescribed dose will be constrained to keep the volume of lung receiving 20 Gy (V20) to be less than 35%. This will be administered in 2.0 Gy daily fractions without a planned treatment break. Treatment will be continuous, 5 days per week for 7-8 consecutive weeks.

**Normal tissue doses:** Dose-volume histograms should be performed for spinal cord, lungs, and heart. The maximal spinal cord dose should not exceed 45 Gy. No more than 35% of the total lung volume should receive greater than 20 Gy. No more than 50% of the total cardiac volume should receive greater than 40 Gy. **The esophagus will be contoured on all patients and the dose volume parameters will be obtained. This is not a dose-limiting structure, and therefore no specific constraints will be mandated.**

## **6.2 Visit 2: Start of Irradiation (Week 0)**

At Visit 2 (Start of Irradiation), toxicity evaluation will be performed and CTCAE scoring determined. Blood, urine, and buccal samples will be obtained. The blood sample obtained will be up to 15mL in volume. Definitive radiation therapy will commence.

## **6.3 Visits 3 to 9(10): Radiation Weeks 1 through 7(8)**

Toxicity evaluation and CTCAE scoring will be obtained. FS compliance will be assessed once each week and FS log will be reviewed.

At approximately 4 weeks following the start of XRT, blood urine, and buccal samples will be obtained. Specimens will be obtained only once at this time point during the course of XRT. The blood sample obtained will be up to 15mL in volume

Subjects will be instructed not to eat their FS within 4 hours before radiation, and preferably after radiation treatment on those days. Subjects will be instructed to stop eating FS at the completion of their prescribed radiotherapy.

## **6.4 Post Radiation 1 Month Follow-up**

Toxicity evaluation and CTCAE scoring will be performed, with bloodwork being performed as clinically indicated as part of standard of care. Urine and blood sampling for urinary isoprostanes and plasma FS lignan levels will be assessed. A buccal swab will also be obtained.

## **6.5 Post Radiation 6 Month Follow-up**

Toxicity evaluation and CTCAE scoring will be performed, with blood work being performed as clinically indicated as part of standard of care. Study cessation will be at the 6-month post XRT visit.

CONFIDENTIAL

This material is the property of the University of Pennsylvania. Do not disclose or use except as authorized in writing by the study sponsor.  
Version Date: 07/27/2017

**Table 1. Study Flow Chart**

Event	Pre-study Eligibility	1 week prior to XRT	Start of XRT	Weekly during XRT	End of XRT	1 month post XRT	6 months post XRT
Visit Week		Visit 1 Week -1	Visit 2 Week 0	Visits 3 to 8(9) Week 1 to 7(8)			
Medical History	X						
Informed Consent	X						
FS Consumption		X*	X*	X*	X*		
FS Log Review		X	X	X	X		
Toxicity Evaluation		X	X	X	X	X	X
FACT-L Questionnaire		X	X	X***	X	X	X
Specimen Collection							
Urine specimen		X**	X	X***	X	X	
Blood specimen		X**	X	X***	X	X	
Buccal Swab		X**	X	X***	X	X	

\*FS consumption to begin after first specimens are obtained approximately 1 week prior to XRT and to continue every day during XRT and end at the end of XRT.

\*\* The first specimen collection can be done any time after consent but prior to first FS consumption.

\*\*\*Specimen collection and FACT-L questionnaires during XRT will occur at one time point only (approximately 4 weeks following the start of XRT)

## 7 Statistical Plan

### 7.1 Study Design

This is a single arm phase II flaxseed diet supplement for subjects with locally advanced or metastatic NSCLC who are scheduled to begin conventional chemoradiation therapy with definitive intent. Flaxseed is thought to be a protectant for radiation pneumonitis. Subjects will be told to ingest 40g of flaxseed daily.

FS will be ingested daily for 8-9 weeks, including 7-8 weeks during radiation and for 1 week prior to radiation. Subjects will be queried weekly about their FS consumption while on the diet. Serial measurements of plasma levels of flaxseed metabolites, urine levels of oxidative stress markers, and buccal swabs will be obtained at 5 time points: baseline (prior to start of radiation), at week 0 of radiation, 4 weeks into radiation, at the end of radiation and at one month post-radiation. This assessment is important because NSCLC subjects receiving radiation therapy often develop esophagitis and swallowing difficulties.

CONFIDENTIAL

This material is the property of the University of Pennsylvania. Do not disclose or use except as authorized in writing by the study sponsor.  
Version Date: 07/27/2017

## 7.2 Statistical Analyses and Decision-making

Primary Objective: This is a single-arm phase II trial. The primary endpoint will be absence of radiation pneumonitis (RP) of grade 3 or above within 6 months from the end of RT, according to the CTCAE v.4.0 scale. The most recent pooled Radiation Therapy Oncology Group analysis showed that the rate of  $\geq$  grade 3 RP was 18%, so the null hypothesis “clinical response” rate for this study is 82%. A sample size of n=39 achieves 80% power to detect a response rate of 94.1% in a one-sided binomial exact test with target significance level no larger than  $\alpha=0.1$ . The actual significance level achieved by this test is 0.062. We will reject the null hypothesis that FS treatment has no effect on the RP rate if there are 3 or fewer cases of RP in the 39 evaluable subjects. Assuming a death rate of 10% prior to 6 months and a 10% inevaluable rate, **we will seek to enroll 48 patients**. As the Department of Radiation Oncology at Penn is one of the busiest centers in the country and currently treats approximately 235 patients daily, and the thoracic oncology service is the busiest clinic service within the Department and has exceptional rates of enrollment of patients onto investigator-initiated clinical trials, we expect to have no difficulty enrolling 48 patients in two years.

Secondary Objective: We will analyze the continuous secondary endpoints (Aim 2) using mixed linear models that include random effects for subject. We will inspect the data before analysis to identify a transformation to normality, if needed. A simpler form of the analysis would be to conduct a paired *t* test comparing baseline to post-treatment values. With n=39 evaluable subjects, we will be able to detect a change in the mean of 0.533 standard deviations with 90% power in a two-tailed test with type I error rate  $\alpha=0.05$ . We will collect blood and urine for markers of antioxidant activity and systemic inflammation, and buccal swabs for antioxidant enzyme epithelial gene expression at the specified time points. We will analyze the data using mixed linear models that include random effects for subject. This will effectively be the same as a paired *t*-test on differences across the treatment periods.

Multiplicity: We will take an intermediate approach to avoid potential spurious claims of statistical significance due to the multiplicity of outcomes. We will consider the sets of outcomes — antioxidant activity, epithelial gene expression, and clinical safety and efficacy — separately, adjusting for multiplicity as needed within each by the Simes procedure, which is more powerful than Bonferroni but provides the same level of control for the family-wise error rate.

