## Study Summary

Title	PHASE II TRIAL OF FLAXSEED TO PREVENT PNEUMONOPATHY AFTER CHEMORADIATION FOR LUNG CANCER
Short Title	Dietary Flaxseed in NSCLC
Protocol Number	
Phase	Phase II
Methodology	Single-arm study, 40g flaxseed ingested per day
Study Duration	Two years
Study Center(s)	Single-center
Objectives	To establish the utility of FS supplementation in patients receiving chemoradiation therapy for lung cancer; To validate the ability to measure biomarkers of oxidative stress and active FS metabolites in these patients; to quantify oxidative stress.
Number of Subjects	48 subjects
Diagnosis and Main Inclusion Criteria	Patients with locally advanced or metastatic non-small cell lung cancer (NSCLC) receiving chemoradiotherapy with definitive intent
Study Product, Dose, Route, Regimen	Whole grain flaxseed diet consisting of 40g flaxseed ingested per day
Duration of administration	Approximately eight to nine weeks
Reference therapy	none
Statistical Methodology	This is a single-arm phase II trial. The primary endpoint will be absence of radiation pneumonitis (RP) of grade 3 or above within 6 months from the end of XRT, according to the CTCAE v.4.0 scale. The most recent pooled Radiation Therapy Oncology Group analysis showed that the rate of $\geq$ grade 3 RP was 18%  , so the null hypothesis “clinical response” rate for this study is 82%. A sample size of n=39 achieves 80% power to detect a response rate of 94.1% in a one-sided binomial exact test with target significance level no larger than $\alpha=0.1$ . The actual significance level achieved by this test is 0.062. We will reject the null hypothesis that FS treatment has no effect on the RP rate if there are 3 or fewer cases of RP in the 39 evaluable subjects. Assuming a death rate of 10% prior to 6 months and a 10% inevaluable rate, we will seek to enroll 48 patients.

CONFIDENTIAL

This material is the property of the University of Pennsylvania. Do not disclose or use except as authorized in writing by the study sponsor.  
Version Date: 07/27/2017

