### 1.1 Background

The effectiveness of radiotherapy for thoracic malignancies is limited by the high radiosensitivity of normal lung parenchyma. Clinically significant radiation lung injury occurs in up to 30% of patients irradiated for lung cancer and 10-15% of other thoracic oncology patients. A greater proportion of patients have subclinical adverse effects of radiation on the lung, identifiable by imaging and/or physiologic testing. Highly reactive compounds known as reactive oxygen species (ROS) and reactive nitrogen species (RNS) are induced in large quantities by radiation therapy (XRT) and have been implicated in this form of lung injury.

Two phases of radiation-induced lung injury have been described in humans. Acute radiation pneumonitis, thought to be largely inflammatory and exudative in nature, can occur several weeks to six months post-irradiation, and can be life threatening if a large volume of lung has been affected. In the second phase of radiation-induced lung injury that can occur months to years after irradiation, the lung tissue enters a fibrotic state in which the numbers of inflammatory cells decrease and a marked thickening of alveolar walls occurs due to collagen deposition.

There is currently no known effective pharmacologic therapy for the prevention of acute or chronic radiation pneumonopathy. Systemic oral and intravenous corticosteroids are routinely used to treat clinically significant acute radiation pneumonitis, but the administration of these drugs does not alter the risk of developing late radiation fibrosis. The exact mechanism by which the acute radiation pneumonitis phase transitions to the late fibrotic phase is unclear. However, as recently reviewed by Robbins and Zhao, studies implicate a chronic state of oxidative stress in radiation-induced late fibrosis; it is widely recognized that irradiation is associated with both a rapid and a chronic increase in ROS/RNS production. This persistent state of oxidative stress may therefore be a target for inhibition of radiation injury and radioprotection of normal tissues to allow for more effective radiotherapy and improved clinical outcomes.

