##### **4.4.2 Data Collection and Follow-up for Withdrawn Subjects**

Even though subjects may be withdrawn prematurely from the study, toxicity data will continue to be assessed as part of the normal radiotherapy protocol as determined by the investigator. Routine tests will be performed as standard of care as part of the ongoing radiotherapy.

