## 7.3 Sample Size and Study Duration

A maximum of 48 subjects with locally advanced or metastatic NSCLC who undergo definitive chemoradiation will be accrued over approximately two years. The study will close when the final subject has undergone the approximately 6-month post-radiation follow-up visit.

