## 7.4 Subject Population(s) for Analysis

The all-treated population will be used for all study analyses. For purposes of this study, the all-treated population is defined as the group of subjects ingesting at least 1 week of FS.

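### The primary rule (3 or fewer RP cases in 39 undefined evaluable subjects) does not match the population that Section 7.4 names for all analyses, and its stated alpha and power hold at n=39 only

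*Combined protocol and SAP*

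**What the plan says.** Section 7.2 defines the primary endpoint as freedom from grade 3 or higher RP within 6 months of the end of radiotherapy. It tests a null response rate of 82% (RP 18%) against 94.1% (RP 5.9%) with a one-sided exact binomial test at a level of at most 0.1. The null hypothesis is rejected "if there are 3 or fewer cases of RP in the 39 evaluable subjects". The stated attained alpha is 0.062 and the stated power 80%. The Study Summary repeats the rule: "3 or fewer cases of RP in the 39 evaluable subjects".

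Enrolment is set at 48 on this basis: "Assuming a death rate of 10% prior to 6 months and a 10% inevaluable rate". Section 7.3 makes that a ceiling: "A maximum of 48 subjects with locally advanced or metastatic NSCLC".

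Section 7.4 then states: "The all-treated population will be used for all study analyses". Its definition is that "the all-treated population is defined as the group of subjects ingesting at least 1 week of FS". It sets no condition on survival, follow-up or RP assessment at 6 months.

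The documents do not define evaluable, give no cut-off for any n other than 39, and do not say how a treated subject who dies or is lost before 6 months is counted. For withdrawn subjects, Section 4.4.2 says that "toxicity data will continue to be assessed as part of the normal radiotherapy protocol as determined by the investigator".

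**The concern.** The sections point to different denominators for the trial's one formal efficacy decision. The step from 39 to 48 in Section 7.2 implies that early deaths and inevaluable subjects lie outside the 39. Section 7.4, as worded, keeps most of them, because one week of FS is completed at about the start of radiotherapy.

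A count of 3 is calibrated to 39 subjects at risk. If the denominator grows and the added subjects can have RP, the same count is a stricter test. Some of them could. Section 1.1 says that acute RP "can occur several weeks to six months post-irradiation", so a subject lost part-way through follow-up may already have had it, and Section 4.4.2 leaves room for it to be recorded.

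At stake are the power of the primary test and whether two analysts following the same plan would use the same denominator. The trial is single-arm and open-label, so a choice left open until outcomes are known is hard to defend afterwards.

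**Working it through.** **Inputs.** From Section 7.2: RP rate 0.18 under the null and 0.059 under the alternative, n=39, cut-off 3, alpha limit 0.10, 10% deaths and 10% inevaluable. From Section 7.3: at most 48 enrolled. Assumed: all 48 reach one week of FS (a maximum), 9 are lost (48 − 39), and each lost subject has a fraction f of the full RP risk. The documents give no f, so it runs from 0 to 1.

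**1. The plan's own figures.** With X the number of RP cases:
- alpha = P(X ≤ 3 | n=39, p=0.18) = 0.0618
- power = P(X ≤ 3 | n=39, p=0.059) = 0.804

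Both agree with Section 7.2. The enrolment step is consistent too: 39/(0.9 × 0.9) = 48.1, or 39/0.8 = 48.75. Retention is therefore 80 to 81%, and 48 enrolled give an expected 38.4 to 38.9 evaluable.

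**2. Cut-off of 3 applied to 48 treated subjects.** X is the sum of Bin(39, p) and Bin(9, f·p).

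| f | alpha | power |
|---|---|---|
| 0 | 0.062 | 0.804 |
| 0.25 | 0.047 | 0.775 |
| 0.5 | 0.035 | 0.746 |
| 0.75 | 0.025 | 0.716 |
| 1 | 0.018 | 0.686 |

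The largest power loss is 0.804 − 0.686 = 0.118, about 12 points. With fewer treated subjects it is smaller: at n=42 and full risk, alpha/power are 0.042/0.766.

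**3. Cut-off of 3 applied to an evaluable n other than 39.** The last two columns give the largest cut-off with alpha at most 0.10, and its operating characteristics.

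| n | cut-off 3: alpha/power | largest valid cut-off | its alpha/power |
|---|---|---|---|
| 30 | 0.186/0.902 | 2 | 0.074/0.741 |
| 35 | 0.103/0.851 | 2 | 0.036/0.659 |
| 36 | 0.091/0.839 | 3 | 0.091/0.839 |
| 42 | 0.042/0.766 | 3 | 0.042/0.766 |
| 43 | 0.036/0.753 | 4 | 0.093/0.892 |
| 48 | 0.018/0.686 | 4 | 0.051/0.848 |

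So 3 is the right cut-off for n=36 to 42, 2 for n=30 to 35, and 4 for n=43 to 48.

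**4. How often n falls outside 36 to 42.** With evaluable n ~ Bin(48, 0.80) or Bin(48, 0.81):
- n ≤ 35: 0.148 or 0.110
- n = 36 to 42: 0.790 or 0.805
- n ≥ 43: 1 − 0.148 − 0.790 = 0.062, or 1 − 0.110 − 0.805 = 0.085

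**5. The proposed definition of evaluable.** An early loss counts only if RP was recorded. With k subjects followed to 6 months (completers) and x RP cases among the 48 − k lost, n = k + x and the cut-off is the one for that n. With k=39, alpha/power are 0.062/0.804, 0.035/0.746 and 0.018/0.686 at f = 0, 0.5 and 1. Over k=30 to 48 and f from 0 to 1, the largest alpha is 0.0927 (k=43, f=0).

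**The case against.** The best defence is that a specific rule governs a general one. Section 7.2 names the denominator for this decision, explains the gap to 48, and uses 39 evaluable subjects again for the secondary analysis. Section 7.4 can then be read as an exposure requirement on top. This is a natural reading and it removes the conflict. However, Section 7.4 refers to all analyses and never mentions evaluability, and this reading still leaves evaluable undefined and the cut-off tied to one value of n.

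Two further points stand. Section 4.4.2 ties continued assessment to the normal course of radiotherapy and does not promise RP ascertainment to 6 months, so recorded RP among lost subjects may be rare; at f=0 the stated figures are unchanged. The figure of 48 treated is also an upper limit. Section 4.4.1 allows withdrawn subjects to be replaced, but within the ceiling of 48.

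A reader might infer that Section 7.4 inflates the false-positive rate or could reverse the result. With four RP cases, the exact p-value is 0.145 at n=39 and 0.051 at n=48. If the test were re-run at 48 with a cut-off of 4, alpha would be 0.145 when the 9 lost subjects can show no RP. The documents do not support this reading, because they contain no such re-run: the only stated cut-off is 3, and in the all-treated set that lowers alpha.

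**Conclusion.** The concern holds as an unresolved mismatch that should be fixed before the primary analysis. The arithmetic at n=39 is correct; what is missing is a single named population, a definition of evaluable, and a rule for any other n.

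If Section 7.4 is followed literally with the stated count, the error is conservative: alpha falls from 0.062 to as low as 0.018 and power from 0.804 to as low as 0.686. The size depends on the assumed RP risk in lost subjects and on all 48 being treated.

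If the evaluable reading is adopted, the rule is sound for n=36 to 42, which is 79 to 81% likely. It exceeds the plan's own 0.10 limit at n of 35 or fewer (11 to 15% likely) and gives up power at n of 43 or more. These probabilities assume independent attrition at the plan's planning rates.

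It would also be wrong to infer that defining evaluable restores 80% power in every case. With 39 completers, the definition proposed below has the same power as 3 of 48: 0.746 at half risk and 0.686 at full risk. The gain is one unambiguous rule with alpha controlled.

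**What to change.** - **(a) Population.** In Sections 7.2 and 7.4 and the Study Summary, name the evaluable subset of the all-treated set as the primary population, and define it. One option: at least one week of FS, and either grade 3 or higher RP (fatal RP included) by 6 months after radiotherapy, or an assessment at 6 months showing none. Other definitions are possible; the essential step is to fix one in advance. Report the all-treated set as a sensitivity analysis.
- **(b) Decision rule.** Replace the fixed 3 of 39 with the exact one-sided binomial test against 18% at level 0.10, at the attained evaluable n: 2 or fewer for n=30 to 35, 3 or fewer for n=36 to 42, 4 or fewer for n=43 to 48. Do not apply these cut-offs to a denominator that counts lost subjects as RP-free.
- **(c) Operating characteristics.** Restate alpha and power for that population.

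**Cost.** Wording in three places and no extra patients. The example definition is conservative, because early losses enter the denominator only if they had RP. With random attrition at 80 to 81% retention, alpha/power are 0.063/0.79–0.80 at zero risk in the lost, 0.036–0.037/0.74 at half risk, and 0.020–0.022/0.68–0.69 at full risk. Power is about 66 to 74% if the evaluable n falls to 30 to 35. In return, alpha stays at or below 0.093 for 30 to 48 completers and any risk in the lost from zero to full.
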